#### **Interim Data Analysis Stage 1**

Upon successful completion of approximately 70% of the originally planned PICV placements in Stage 1, an interim analysis of the primary endpoint on raw (uncleaned) data will be performed. The observed complication rate in Stage 1, utilizing actual data collected in the study up to this point, will be compared to the originally estimated complication rate of 50%. If the observed complication rate is statistically significantly greater than 50%, the sample size will not be modified, and Stage 1 enrollment will continue to the original sample size of at least 316 successful PIVC insertions. If the observed complication rate is not statistically significantly greater than 50%, the sample size may be re-estimated with the assumed Stage 1 complication rate equal to the observed interim analysis complication rate, with other assumptions held constant.

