## 1 INTRODUCTION

B. Braun Medical Inc. (B. Braun) is committed to enhancing clinical outcomes while managing workflow efficiencies. B. Braun leads the way in developing infusion therapy and pain management products and services that meet the highest standards for quality, safety, efficiency and sustainability.

Peripheral intravenous catheters (PIVCs) are used to deliver medication and fluids directly into the bloodstream. The placement of PIVCs is the most common invasive hospital procedure. In the United States (US) alone, more than 300 million PIVCs are sold each year and 60% to 90% of hospitalized patients require an IV catheter (Helm, 2015). Despite the large medical demand for PIVCs, there is a high failure rate and large cost associated with replacing the catheter due to complications, not counting the need to perform unnecessary PIVC insertions.

The Centers for Disease Control and Prevention (CDC) recommends rotating the PIVC site at 72 to 96-hour intervals to reduce the risk of infection and patient discomfort associated with phlebitis (O'Grady, 2002). However, typical catheter dwell times range from only 1.9 to 2.5 days (Powell, 2008; Royer, 2003; Sheppard, 1999). Failures, which occur in anywhere from 35% to 70% of PIVCs, take the forms of phlebitis, infiltration, occlusion/mechanical failure, dislodgment, and infection (Helm, 2015; Maki, 1991; Shears, 2006). A PIVC failure is considered to have occurred when the PIVC stops working safely before the end of the 72 to 96-hour limit or before the end of its intended dwell time (PIVC is no longer needed). These failures are associated with many factors, including the products used and the expertise of the clinician inserting and maintaining the PIVC, and add to the costs of intravenous (IV) therapy (Helm, 2015).

While the initial cost of inserting a PIVC in the US is roughly between \$28 and \$35 for “first-stick” insertions, the costs of identifying, inserting, and removing a PIVC is repeated each time a failed catheter is replaced (Helm, 2015; Rickard, 2012; Webster, 2008). Additional costs come from treating the PIVC complications such as bleeding, hematoma formation, infusate extravasation, thrombophlebitis, and catheter-related bloodstream infection (Smith, 1998; Greig, 2002; Doellman, 2009; Hollenbeak, 2012).

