### **12.4 Determination of Sample Size**

Based on initial study design assumptions, at least 316 successful PIVC insertions are necessary to complete Stage 1 and at least 316 successful PICV insertions are necessary to complete Stage 4 in order to detect a statistically significant difference between the current standard-of-care and B. Braun PA at 90% power and two-sided confidence level of 5.0%. The estimated complication rate in Stage 1 is 50% and the estimated complication rate in Stage 4 is 35%. ([Helm, 2015](#))

Two interim analyses are planned, solely for the purpose of sample size re-estimation. Using the method of Pocock & Mehta, the sample size can be either held constant or increased – it cannot be reduced based on the results of the re-estimation.

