#### **Interim Data Analysis Stage 4**

The final sample size in Stage 1 (based on the results of the sample size re-estimation in Stage 1) will be used as the initial sample size for Stage 4. Upon successful completion of approximately 50% of the initial sample size in Stage 4 (which is determined at the interim analysis in Stage 1), another interim analysis on raw (uncleaned) data for the complications will be performed. This sample size re-estimation will follow the method of Mehta and

Pocock to calculate the conditional power of the study to conclude that the complication rate in Stage 4 is lower than the complication rate in Stage 1, given the observed complication rates at the interim analysis. The conditional power (CP) will be categorized into one of the three following zones:

- Favorable:  $CP \geq 90\%$
- Promising:  $41\% \leq CP < 90\%$
- Unfavorable:  $CP < 41\%$

In the event the conditional power is found to be in the Favorable or Unfavorable zone, the study will continue to the originally planned sample size in Stage 4 (i.e., final sample size in Stage 1). In the event the conditional power is in the Promising zone, the total study sample size may be increased to the required sample size to achieve conditional power of 90% at the completion of the study. Note that only the sample size in Stage 4 can be increased at this time, as the data collection in Stage 1 has been completed.

**Registered nurses:** Only RNs from the hospital's ED or medical surgical departments/unit will participate. Registered nurses can be on any shift and will not be required to have a minimum level of clinical experience. There is no minimum number of RNs required.

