## **18 TERMINATION OR SUSPENSION OF STUDY**

Both B. Braun and the Investigator reserve the right to terminate or suspend the study at any time. If early study termination is necessary, study procedures will be completed on an individual subject basis after review and consultation by both B. Braun and the Investigator. In terminating the study, B. Braun and the Investigator will ensure that adequate consideration will be given regarding the protection of the subjects' interests.

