#### **9.1.2. *Interim Data Analysis Stage 4***

The final sample size in Stage 1 (based on the results of the sample size re-estimation in Stage 1) will be used as the initial sample size for Stage 4. Upon successful completion of approximately 50% of the initial sample size in Stage 4 (which is determined at the interim analysis in Stage 1), another interim analysis on uncleaned data for the complications will be performed. This sample size re-estimation will follow the method of Mehta and Pocock to calculate the conditional power of the study to conclude that the complication rate in Stage 4 is lower than the complication rate in Stage 1, given the observed complication rates at the interim analysis. The conditional power (CP) will be categorized into one of the following three (3) zones:

- Favorable:  $CP \geq 90\%$
- Promising:  $41\% \leq CP < 90\%$
- Unfavorable:  $CP < 41\%$

In the event the conditional power is found to be in the Favorable or Unfavorable zone, the study will continue to the originally planned sample size in Stage 4 (i.e., final sample size in Stage 1). In the event the conditional power is in the Promising zone, the total study sample size may be increased to the required sample size to achieve conditional power of 90% at the completion of the study. Note that only the sample size in Stage 4 can be increased at this time, as the data collection in Stage 1 has been completed.

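### Does the lack of a maximum in the two sample-size re-estimation rules call for a change to the plan?

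*Protocol*

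**What the plan says.** Protocol section 12.4 plans 316 successful placements per stage for 90% power at two-sided 5%: "The estimated complication rate in Stage 1 is 50% and the estimated complication rate in Stage 4 is 35" (per cent). Of the size, it says that "it cannot be reduced based on the results of the re-estimation".

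**Stage 1.** At about 70% of the planned placements, if the observed rate is not significantly above 50%, the size may be recomputed "with the assumed Stage 1 complication rate equal to the observed interim analysis complication rate, with other assumptions held constant". SAP 9.1.1 repeats this. The final Stage 1 size becomes the starting size for Stage 4.

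**Stage 4.** At about half of that starting size, conditional power is computed "given the observed complication rates at the interim analysis" (SAP 9.1.2). Between 41% and 90%, the "total study sample size may be increased to the required sample size to achieve conditional power of 90% at the completion of the study". The protocol adds that "only the sample size in Stage 4 can be increased at this time, as the data collection in Stage 1 has been completed".

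Neither document gives a maximum, a minimum difference, or a rule for an observed Stage 1 rate of 35% or less. Protocol section 18 lets the sponsor and the investigator "reserve the right to terminate or suspend the study at any time".

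**The concern.** The only rate besides the 50% in the sample-size section is the 35% for Stage 4, so keeping everything else constant appears to fix it. The assumed benefit then shrinks as the observed baseline falls. Because the size varies with the inverse square of that difference, it grows without limit towards 35%. Below 35% a symmetric two-sided formula returns finite sizes for a difference in the wrong direction.

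The Introduction makes a low baseline conceivable: "Failures, which occur in anywhere from 35% to 70% of PIVCs". Failure is not identical to the complication endpoint, but this is the documents' own range and its lower end is where the rule breaks down. An enlarged Stage 1 also carries into Stage 4, which has its own unlimited increase. At stake are feasibility and a judgement made after complication data have been seen.

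**Working it through.** **The plan's own figure.** The documents do not give the formula. I assume the usual pooled two-proportion formula, with p = (p1 + p4)/2:

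n = [z_a √(2p(1−p)) + z_b √(p1(1−p1) + p4(1−p4))]² / (p1 − p4)²

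For 50% v 35%, two-sided 5%, 90% power: (1.960 × 0.6991 + 1.2816 × 0.6910)² / 0.0225 = 5.089 / 0.0225 = 226.2, so 227 per stage, not 316. At 316 the power is 97%. The growth ratios below are therefore firmer than the absolute sizes.

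**Stage 1, with p4 held at 35%.**

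| Observed Stage 1 rate | n, two-sided 5% | n, one-sided 5% (SAP 9.2.10) | Multiple of the 50% value |
|---|---|---|---|
| 50% | 227 | 185 | 1 |
| 45% | 503 | 410 | 2.2 |
| 42% | 1,014 | 826 | 4.5 |
| 40% | 1,969 | 1,604 | 8.7 |

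For example, at 40%: (1.960 × 0.6847 + 1.2816 × 0.6837)² / 0.0025 = 4.920 / 0.0025 = 1,968.1. At 36% the two-sided size is 48,117, and at 35% it is undefined. On this formula the computed size is below 316 whenever the observed rate is above about 47.7%, and the floor then applies.

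**How likely is this?** The interim falls at 0.70 × 316 ≈ 221 placements. From the binomial distribution, two-sided sizes:

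| True Stage 1 rate | P(observed ≤ 35%), 77 or fewer | P(n > 1,000 or no valid n), 92 or fewer |
|---|---|---|
| 50% | 0.0004% | 0.8% |
| 45% | 0.14% | 17% |
| 40% | 6.6% | 71% |

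The last column is almost entirely large but finite sizes. If the curve is scaled so that 50% v 35% gives 316 (an assumption), it becomes about 2%, 30% and 84%.

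**Stage 4.** The conditional-power formula is not written out, so I tried two. Both take 316 completed in Stage 1 and 158 at the Stage 4 interim.

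1. *Given the completed Stage 1 rate of 50%.* CP = Φ[(p1 − p4 − z·se)/sd], with se = √(p1(1−p1)/316 + p4(1−p4)/N4) and sd = √((N4 − 158) p4(1−p4))/N4. At z = 1.96, CP is 41% when p4 is 42.7%, and 90% then needs N4 ≈ 1,956. At z = 1.645 it needs about 2,714. These are 6.2 and 8.6 times 316. From 75% conditional power, about 580 or 630 are enough.
2. *Interim z, with information 1/(1/316 + 1/N4).* The information fraction at the interim is 105.3/158 = 0.667, so CP of 41% corresponds to z = 1.493. As N4 grows the fraction tends to 105.3/316 = 1/3, and CP tends to Φ[(1.493 × 1.732 − 1.96)/0.8165] = 78%. At z = 1.645 the ceiling is 73%. From the 41% edge, 90% cannot be reached at any size.

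**What a ceiling would do.** With 632 per stage, power is 73% for 42% v 35% and 45% for 40% v 35% (two-sided), or 82% and 58% (one-sided). With a Stage 4 ceiling of 632 under formula 1, 90% is reached only from conditional power of about 72% (z = 1.96) or 75% (z = 1.645), and the 41% edge rises to 63% or 60%. If Stage 1 had itself grown to 632, a Stage 4 ceiling of 632 would leave no room for any increase.

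**The case for a change.** The strongest case for a change is that permission is not a limit. The study is open-label and has no data monitoring committee (SAP 6.1.3 and 9.2.4), so what to do with an unworkable size would be decided after complication data are seen. A stated maximum would remove that judgement at the cost of a few words. The constant-assumptions wording could also mean a 15-point difference. The formula then gives 227 at 50% and 203 at 40%, both below the floor of 316, so re-estimation would not raise the size at those rates. A reader could fairly ask which reading is meant.

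The missing ceiling, the ambiguity and the discretion all stand. Their consequences are limited. At the Stage 1 interim no Stage 4 data exist, because each stage must finish before the next begins. A decision there to hold the size cannot be steered by the observed comparison. At the Stage 4 interim, declining to increase leaves the planned size in place.

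The lower edge of the promising zone does depend on how far the study may grow. Under formula 2 with a maximum of 632, an increase stops raising type I error from a conditional power of about 42% (z = 1.96) or 43% (z = 1.645), against the stated 41%. Any effect there would be small.

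An obvious remedy also has its own cost. Applying the maximum at every observed rate of 35% or less would commit the largest study exactly where the assumed benefit is nil or negative.

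**Conclusion.** No change is called for. Neither document states a ceiling, and the computed Stage 1 size rises steeply as the observed rate falls: 2.2, 4.5 and 8.7 times the 50% v 35% value at 45%, 42% and 40%. This is an unwritten limit on optional steps. Analysts who obtained an unworkable size, or none, could keep the planned size, and the sponsor could stop the study. The extreme cases need a true baseline of about 40% or less. A ceiling would move the plan from 90% power at uncertain cost to bounded cost at lower power, and statisticians would reasonably differ on that trade.

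The absolute sizes rest on a pooled formula that does not reproduce 316. The Stage 4 multiples rest on a conditional-power formula that the plan does not spell out: one gives about 6 to 9 times the planned size, another makes 90% unattainable from the 41% edge. SAP section 10 records that the study ended before Stage 2 and that no Stage 4 analysis will be done, so a ceiling now would gain nothing for this trial.

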#### **Interim Data Analysis Stage 4**

The final sample size in Stage 1 (based on the results of the sample size re-estimation in Stage 1) will be used as the initial sample size for Stage 4. Upon successful completion of approximately 50% of the initial sample size in Stage 4 (which is determined at the interim analysis in Stage 1), another interim analysis on raw (uncleaned) data for the complications will be performed. This sample size re-estimation will follow the method of Mehta and

Pocock to calculate the conditional power of the study to conclude that the complication rate in Stage 4 is lower than the complication rate in Stage 1, given the observed complication rates at the interim analysis. The conditional power (CP) will be categorized into one of the three following zones:

- Favorable:  $CP \geq 90\%$
- Promising:  $41\% \leq CP < 90\%$
- Unfavorable:  $CP < 41\%$

In the event the conditional power is found to be in the Favorable or Unfavorable zone, the study will continue to the originally planned sample size in Stage 4 (i.e., final sample size in Stage 1). In the event the conditional power is in the Promising zone, the total study sample size may be increased to the required sample size to achieve conditional power of 90% at the completion of the study. Note that only the sample size in Stage 4 can be increased at this time, as the data collection in Stage 1 has been completed.

**Registered nurses:** Only RNs from the hospital's ED or medical surgical departments/unit will participate. Registered nurses can be on any shift and will not be required to have a minimum level of clinical experience. There is no minimum number of RNs required.

**Subjects:** Subjects or their LAR will be consented before participating in Stage 1 and/or Stage 4 and may participate in either, or both, of those stages. Subjects consented for Stage 1 may participate as patients in Stage 3 (Run-In). If the PIVC was removed for a complication, then the subject may not continue or re-enter into the study and he/she is considered a Study Completer. If the PIVC was removed as a result of treatment completion (i.e., subject no longer requires a PIVC) he/she will be considered a Study Completer. In addition, if he/she was subsequently discharged from the facility, then he/she may re-enter the study in the same or different Stage if a re-admission for any reason is required. Subjects who participate in more than one stage, or more than once in a single stage, will be considered independent for all analyses.

## **12.5 B. Braun Peripheral Advantage Program /Visit Compliance**

Any deviations from the protocol will be documented, evaluated and subsequently described in the final study report. A protocol amendment may be required depending on the nature of the deviation.

## **12.6 Demographic and Baseline Characteristics**

Descriptive statistics will be used to summarize demographic/clinical experience information including age, gender, title/function, shift, and years of clinical experience for the RN population. Demographic information including age and gender will be collected from the subject population. No statistical testing to compare the two populations (RNs and Subjects) will be performed.

Demographic and baseline information will be summarized in tables using descriptive statistics.

## **13 STUDY MANAGEMENT**

The Investigator must conduct the study in accordance with the laws and regulations of the country in which the study is conducted and in accordance with the accepted version of the Declaration of Helsinki and/or all relevant federal regulations, as set forth in Parts 50, 56, 312, Subpart D, of Title 21 of the Code of Federal Regulations (CFR), and in compliance with good clinical practice (GCP) guidelines.

Conduct of the study must be approved by an appropriately constituted IRB. Approval is required for the study protocol, any protocol amendments, and ICFs.

### **13.1 Informed Consent**

The Investigator or designee must explain to each subject participating in Stage 1 and Stage 4 the nature of the study, its purpose, the procedures involved, the expected duration, the potential risks and benefits involved, and any discomfort it may entail. Each subject or his/her LAR (if appropriate) must be informed that participation in the study is voluntary, that he/she may withdraw or be withdrawn from the study at any time, and that withdrawal of consent will not affect his/her relationship with the treating physician.

The informed consent should be given by means of a standard written statement, written in non-technical language. The subject or his/her LAR (if appropriate) should read and consider the statement before signing and dating it, and he/she should be given a copy of the signed document. No subject can enter Stage 1 and/or Stage 4 of the study or have any study related procedures performed before informed consent has been obtained from him/her or his/her LAR (if appropriate). A subject may participate in one or more of the 3 Stages that require patient care (Baseline, Run-In, or Post-Interventional). However, subjects must be consented for Stage 1 and/or Stage 4 of the study. In the event a subject re-enrolls in the study, he/she or his/her LAR (if appropriate) must sign another Informed Consent.

The Investigator will provide B. Braun or its representative with a copy of the Institutional Review Board (IRB) approved ICF prior to the start of the study.

### **13.2 Data Handling**

In the event a subject with a successful PIVC insertion drops out or is withdrawn from the study, B. Braun or its designee will be informed in a timely manner and the date and time of withdrawal will be recorded. In the event a subject has or was withdrawn from the study before a PIVC insertion attempt or a successful PIVC insertion by a Study RN, he/she will be considered as an Early Termination from the study. In the event a subject or his/her LAR (if appropriate) withdraws consent or the PI removes the subject from the study for any reason, the subject will be considered as an Early Withdrawal. In the event of a subject's withdrawal of consent or any other early withdrawal that also did not result in the IV being removed, the date and time of that withdrawal will be used as a surrogate for the date and time of removal of the IV and the subject's data will be treated in the same manner as a study completer. In this case, the subjects will not be allowed to re-enroll in the study.

If the PIVC was removed for a complication, then the subject may not continue or re-enter into the study and he/she is considered a Study Completer. If the PIVC was removed as a result of treatment completions (i.e., subject no longer requires a PIVC) he/she will be considered a

Study Completer. In addition, if he/she was subsequently discharged from the facility, then he/she may re-enter the study in the same or different Stage if a re-admission for any reason is required.

Any data to be recorded directly on the eCRFs (to be considered as source data) will be identified at the start of the study. Data reported on the eCRF that are derived from source documents should be consistent with the source documents, or the discrepancies must be explained.

Clinical data will be entered on eCRFs for transmission to the Sponsor. Data on eCRFs transmitted via the web-based data system must correspond to and be supported by source documentation maintained at the study site, unless the study site makes direct data entry to the databases for which no other original or source documentation is maintained. In such cases, the study site should document which eCRFs are subject to direct data entry and should have in place procedures to obtain and retain copies of the information submitted by direct data entry (such as diaries). All study forms and records transmitted to the Sponsor must carry only coded identifiers such that personally identifying information is not transmitted. The primary method of data transmittal is via the secure, internet-based EDC system maintained by the Contract Research Organization. Access to the EDC system is available to authorized users via the study's Internet web site, where an assigned username and password are required for access.

Any changes made to data after collection will be made through the use of electronic data clarification forms/queries. eCRFs will be considered complete when all missing and/or incorrect data have been resolved.

### **13.3 Source Documents**

Source documents are considered to be all information in original records and certified copies of original records of clinical findings, observations, data or other activities in a clinical study necessary for the reconstruction and evaluation of the study.

